## **9. ETHICAL ISSUES**

### **9.1 Ethical and regulatory review**

This clinical trial will be submitted to the Institutional Review Board for formal review and approval. of the ITM, the CE of the University Hospital of Antwerp and the relevant ethics committees in the DRC. No

specific intervention will not take place until written approval has been obtained from the study committees.

ethics, compliance with local regulatory requirements and signature of the clinical study protocol. of each contractual party involved. Ethics committees to be kept informed of progress

~~The study informed of the study's compliance with current national and international regulations, including~~

including CIOMS international ethical guidelines for biomedical research involving human subjects (16), the Declaration of Helsinki (17), the harmonized tripartite directive for ICH Good Clinical Practice E6 (ICH-E6) (14), the WHO GCLP (15) and the

~~Nagoya 18~~ will also be included in the public registry [Clinicaltrials.gov] before recruitment begins. of participants.

### **9.2 Protocol changes**

Once the final clinical study protocol has been issued and signed by the authorized signatories, it cannot be used for any other purpose.

can be amended informally. Amendments to the protocol have the same legal status and must pass through the appropriate stages before being implemented. Any modification substantial must be approved by all the organizations and CEs that have approved the protocol before it is implemented, unless it is due to concerns about the safety of participants (in which case immediate implementation may be necessary to protect participants). If changes to the protocol or an amendment are requested by an EC/CA during the review process, they must be discussed and agreed with the promoter before any new submission incorporating these changes.

### **9.3 Informed consent**

No participant may be admitted to the study until the investigator or designated person has obtained the written informed consent form.

### **9.4 Privacy policy**

Individual medical information collected in this study will remain confidential. Visit members of the study team are bound by professional secrecy. The data

will be made available to doctors in charge of patients on request to the investigators. Disclosure to third parties is strictly forbidden. The electronic files will not contain any data that could allow the identification of the customer (e.g. surname, first name, full date of birth, telephone number). Each participating in the study will be assigned a unique identification code (ID). On all documents or study files, study participants will be identified by the participant identification code. At each clinical site, a correspondence list will establish the link between the participant ID and the personal data of the participant so that the results of the examinations can be used for the patient care. This list containing personal data and other documents containing the names or signatures of participants (e.g., informed consent) will be retained separately from other study documents. All study documents will be stored in a secure, locked area, with access limited to the site's principal investigator and staff authorized. Access to all paper documents and electronic files required for data management and monitoring of the study will be limited to authorized personnel, at international, regional and local levels. The study computers and the eCRF files will only be accessible via a connection with a user name and a personal password. A list of authorized users of eCRF and the database will be kept at ITM and updated throughout the study.

## **9.5 Risks and benefits**

A venous +/- capillary blood sample is part of the study procedures, but is in any case also necessary in the clinical management of most patients. The 2 samples will be integrated. Sampling can be uncomfortable, even painful. Visit risk of complications from blood sampling is very low (may include haemorrhage in elderly patients), people with coagulation disorders, puncture site infection or thrombosis (superficial veins). The amount of blood to be collected for this study, both for routine and additional analyses, in no case exceeds the maximum of what is considered acceptable as safe for the patient. In any case, routine analyses for management will always be priority, if sufficient volume cannot be achieved. The greatest risk for participants is a potential breach of confidentiality of data, for which all measures will be put in place to limit them as much as possible. Apart from access to laboratory analyses that can improve management (some research biomarkers), there are no advantages to participating in the study. Compensation is still provided for a requested trip, this compensation does not exceed the usual burden of effort.

## **9.6 Incidental discoveries**

All results of immediate laboratory analyses in the FIKI study (with the exception of TDR for dengue fever, currently being evaluated in the African context) will be communicated to the team, the patient. In general, these are analyses that should already be part of the routine management of febrile illnesses.

As explained above, however, participation in the study can lead to chance discoveries. pathogens that can give rise to chronic infections (asymptomatic for long periods),

requiring further action at the level of the individual patient. These discoveries can occur in metagenomic sequencing and secondary research.

If an endemic infection with immediate importance for management such as trypanosomiasis is detected during secondary research, the patient and medical team will be informed, and the patient will be offered a free diagnostic evaluation (and possible treatment) at a nearby referral center.

If a chronic infection (HIV, HBV, HCV, etc.) is discovered incidentally during the analyses metagenomics or subsequent secondary research), only the results considered to be will be communicated. The results of this technique are not considered conclusive for the time being (the metagenomic analysis currently being development is not yet a validated clinical laboratory test) and would require a additional confirmation through a standard clinical workup. The study teams will then be responsible for informing the participant in question and directing him or her to the care structure appropriate for the health problem detected.

## **9.7 Compensation for participation**

There is no compensation for participation in the study. Patients who cannot be contacted by telephone and who return to the study center on days 7, 14 and 21 will receive a amount sufficient for a round trip using standard means of transport in addition to any daily allowance, in line with that given by similar studies on this site, and approved by local ethics committees.

## **9.8 Insurance**

The coordinator of this study, the Institute of Tropical Medicine, obtained study insurance (without liability) to cover any injury, damage or loss suffered by study participants and which is caused directly or indirectly by their participation in the study.

Information on insurance is not specified in the GSI of this study, due to the fear that of unreasonable claims for compensation. In addition, we do not anticipate any physical injury or mental health problems as a result of participating in this event. observational (non-interventional) study.

## **10. DISSEMINATION OF RESULTS, INTELLECTUAL PROPERTY**

All study documents are provided by the sponsor to the investigators and their staff. confidentiality. None of these documents may be disclosed to any party who is not a not directly involved in the study, without the written authorization of the sponsor.

Once the results are considered final, arrangements will be made for the communicate to the community, in the most appropriate way, with the active participation of health authorities.

Oral communications and written publications must mention the name of the sponsor and the name of the author.

~~All the data and research results will be made in accordance with the CONSORT declaration.~~

[\(<http://www.consort-statement.org/consort-statement>\)](http://www.consort-statement.org/consort-statement)

## **11. ARCHIVING**

The sponsor and the investigator must keep adequate and accurate records to allow for fully document the course of the study and verify study data. Visit relevant (essential) documents are those documents that individually and to assess the progress of the trial, the quality of the data produced and compliance with PCM standards and applicable regulatory requirements. The investigator's file must contain at least all the (essential) documents listed in the "Setting up and maintaining the investigator's file". A copy of all source data and report forms from must always be kept on site.

Once the study has been completed, the study master file (IF) on the site and in the coordination center remain available for internal audits and/or inspections by regulatory authorities for a period of 20 years, unless otherwise requested by the national authorities. The sponsor must be informed before the files are destroyed.

### 13. LIST OF ABBREVIATIONS

ACVPU	alert, confusion, voice, pain, unresponsive'
ALMANACH	'algorithm for the management of childhood illness'.
ALEERRT	the African Coalition for Research, Intervention and Training in the epidemic
AQ	Quality assurance
CA	Competent authorities
CIOMS	Council for international organizations of medical sciences
CFR	Code of Federal Regulations
CONSORT	Consolidated Standards of Reporting Trials
CRC	Clinical Research Center
(e-)CRF	'(electronic -) Case Report Form' - the data collection form
CRP	C-reactive protein
CRSK	Kimpese Health Research Center
CQ	Quality control
DGD	Swiss Agency for Development and Humanitarian Aid
DSMB	Data and Security Control Board
EDCTP	The European & Developing Countries Clinical Trials Partnership
FISSA	'Febrile Illness in sub-Saharan Africa'.
GCP	Good Clinical practice

GCLP	Good clinical laboratory practice
GDPR	General Data Protection Regulation
HGK	Kinshasa General Hospital
HGR	General Reference Hospital (Kimpese)
IC	Investigator Coordinator
IC(F)	Informed Consent (Form) - Formulaire de Consentement Eclairé
ICH	The International Council for Harmonisation - 'Conférence internationale sur harmonization'
(I)CE	Ethics Committee (independent)
IGSA	Simplified ambulatory severity index
IME	Evangelical Medical Institute
ITM	Institute of Tropical Medicine
INRB	French National Institute for Biomedical Research
IRB	Institutional Review Board
MOP	Operating procedures manual
MTA	Material Transfer Agreement
IF	Investigator's File' - main study file
IP	Principal Investigator
WHO/WHO	World Health Organization/Organisation mondiale de la Santé
POC	Point of care
qSOFA	Quick Sepsis Related Organ Failure Assessment
GROUND	Democratic Republic of Congo
FLOOR	Statistical analysis plan
S&P	Checking source data
SOP	Standard Operational Procedure
TDR	Rapid diagnostic tests
TMG	Trial Management Group
EU	European Union
UZA	Universitair Ziekenhuis Antwerpen (~ University Hospital Antwerp)

## 14.

### Appendices Protocol for the evaluation of rapid diagnostic tests for CRP

Background and justification	
Acute febrile illnesses are a major cause of death and disability. morbidity worldwide. In countries with limited resources, they are often treated empirically with antibiotics due to a lack of the absence of reliable diagnostic methods, whereas in most In some cases, this is not necessary. It is well established that inappropriate use of antibiotics, including in the first line of care, contributes to the <del>the rapid potential for bacterial infection</del> marker of inflammation, which can help distinguish between bacterial and non-bacterial causes fever. Currently, rapid diagnostic tests (RDTs) for CRP determination, are becoming increasingly available and can be used to could be very useful in the management of febrile illnesses in primary health care centers. Before evaluating the use of these tests in the routine practice of primary health centers in the DRC, we want to evaluate a selection of 2 immunochromatographic tests (lateral flow) measuring CRP (a qualitative and semi-quantitative) in a controlled laboratory environment.

Design	
Evaluation study of 2 RDTs targeting CRP in the clinical laboratory, as part of the FIKI study

Site and population study	
The study uses existing samples (EDTA blood) from a subpopulation of participants in the FIKI study, and will be carried out in the site laboratory correspondents :
 
 
1. Laboratory of the pediatric emergency department of the Hôpital Général de Kinshasa (HGK)
 
 
<del>Evangelical Central Reference Hospital (ECHR) Laboratory</del>

Objectives and criteria judgment	
Kinshasa Evaluation of the performance of 2 CRP RDTs in comparison with a reference test (QuikRead go®) on patient samples of fever obtained in the FIKI study.
 
Judging criteria
 
 
• degree of correlation between RDTs and reference test (with reading at minimum and maximum time depending on mode)
 
• <del>proportion of valid tests</del>
 
• proportion of migration errors
 
• low background lightening ratio
 
• proportion of test line intensities by scale
 
• degree of inter-observer agreement
 
• degree of repeatability of TDRs
 
• presence of the hook effect for very high CRP values high (> 150 mg/l)
 

Criteria inclusion and exclusion	
2. Assessment of operational features and ease of use 2 CRP RDTs in the laboratory
 
Judging criteria
 
 
systematic analysis of the characteristics of TDRs and their packaging, labelling and instructions for use as per checklist
 
 
Inclusion criteria:
 
 
samples from patients who have given consent for the laboratory part of the FIKI study
 
CRP value (Quikread Go®) according to selection and planned distribution (as described in the 'Selection' section and sample distribution)
 
 
Exclusion criteria :
 
 
samples with a maximum sampling volume of blood (depending on age, weight and Hb, as described in the FIKI study procedures) could not be obtained
 

Selection and distribution of samples	
1. Assessment of correlation between RDTs and reference test, degree of concordance between 2 readers, proportion of invalid tests, errors in migration, low background brightening, and line intensity
 
 
Number of samples planned: 140 (70 per site, adapt to recruitment speed)
 
Distribution 
 
2x14 samples with CRP < 5 mg/L
 
2x14 samples with CRP ≥ 5 - < 10 mg/L
 
2x14 samples with CRP ≥ 10 - < 40 mg/L
 
2x14 samples with CRP ≥ 40 - < 80 mg/L
 
2x14 samples with CRP ≥ 80 mg/L
 
 
 
2 TDR 1x on each sample, with 2 readings by TDR
 
 
2. Evaluation of the croquet effect (HGK only):
 
 
Number of samples: 5
 
Distribution: 5 samples with CRP > 150 mg/L
 
2 TDR 1x on each sample, with 1 reading by TDR
 
 
3. Repeatability assessment (HGK only)
 
 
Number of samples: 5
 
Distribution 
 
1 sample with CRP < 5 mg/L
 
1 sample with CRP ≥ 5 - < 10 mg/L
 
1 sample with CRP ≥ 10 - < 40 mg/L
 
1 sample with CRP ≥ 40 - < 80 mg/L
 
1 sample with CRP ≥ 80 mg/L
 
 
 
2 TDR 5 x on each sample, with 1 reading by TDR
 

Procedures laboratories	
2 RDTs for CRP will be analyzed:
 
 
Qualitative Biopanda® RDT (threshold 10 mg/l)
 
Actim® semi-quantitative RDT (thresholds 10 mg/l, 40 mg/l)
 
 
0 mg/l

	
Reference test for performance evaluation: PoC QuikRead go®. (CRP+Hb kit; range 5-200mg/l ~ hematocrit)
 
Assessment of correlation between RDT and reference test, degree of concordance between 2 readers, proportion of invalid tests, test errors, etc. migration, low background brightening, and line intensity : TDRs will be performed on the EDTA samples of FIKI participants, according to the planned distribution and the producer's recommendations, and read out minimum and maximum incubation times, and also beyond the set time by the manufacturer TDR. Readings will be taken and recorded by two independent readers at the 2 sites and result by Quikread Go. A test result will be considered as invalid when the control line is missing, mottled or irregular. A scale will be used to note the intensity of the line of <del>repeat for each reading</del> for each reading. In case of discrepancy for a test invalid, migration error or poor background illumination, the result of a third reading of the photo by the principal investigator will be taken as a reference.
 
Evaluation of the hook effect, evaluation of repeatability : TDRs will be performed on the EDTA samples of FIKI participants, according to the manufacturer's recommendations. These analyses will only be performed at HGK by the principal investigator of this assessment.
 
Systematic analysis of TDR characteristics and packaging, labeling and instructions for use (based on a checklist of features) will be made and evaluated for ease of use.

Methods analysis	
The kappa index (Cohen's coefficient of agreement) will be used to evaluate the degree of correlation between TDR (reading at minimum, maximum, and reference test for the 2 different readings, and for the inter-observer agreement. With sample size, the distribution and an expected kappa value of 0.6 - 0.7, the interval size of confidence would be 0.184-0.22 (Actim® test) and 0.26-0.30 (Actim® test). Biopanda®) for correlation with the reference test. The proportion of invalid tests, migration errors, clarification of the background At a low level, the intensities of the test lines according to scale will be calculated with the 140 TDRs performed and read at maximum time as the denominator.

Evaluation of the hook effect and repeatability will be carried out in the following way  
descriptive.

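### In the CRP rapid-test repeatability check, only two of the five samples can show imprecision in the qualitative test's result, and the plan leaves their position relative to the cut-off to chance

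*Protocol*

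**What the plan says.** The protocol's appendix on the evaluation of CRP RDTs lists "degree of repeatability of TDRs" among its criteria. Item 3 of its section on selection and distribution of samples plans this part at HGK only: "Number of samples: 5", one per CRP band. The bands start at "1 sample with CRP < 5 mg/L", "1 sample with CRP ≥ 5 - < 10 mg/L" and "1 sample with CRP ≥ 10 - < 40 mg/L", continue with 40 to below 80, and end at "1 sample with CRP ≥ 80 mg/L". The replication is "2 TDR 5 x on each sample, with 1 reading by TDR". No position within a band is required.

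The laboratory procedures give the qualitative RDT one threshold, 10 mg/L. The semi-quantitative RDT has thresholds at 10 and 40 mg/L and a third that is broken in the text available. On who does the hook-effect and repeatability work, they say: "These analyses will only be performed at HGK by the principal investigator of this assessment". Masking to the QuikRead value is not mentioned. The analysis is descriptive, with no acceptance limit.

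**The concern.** A positive/negative result varies between replicates of one sample mainly when that sample is near the cut-off. Five replicates of a sample far from 10 mg/L will agree on the qualitative RDT whether the device is precise or not. If the two samples that could be informative also happen to fall far from 10, a clean repeatability result carries little evidence. If they happen to fall right beside it, even a good device will show disagreement. The reported repeatability then reflects the choice of samples as much as the test. The appendix is meant to inform a later evaluation of these tests in primary health centres, so it is useful for the repeatability result to be interpretable.

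**Working it through.** **Inputs.** From the appendix: five samples, five replicates per RDT, one reading, so 5 × 5 = 25 results per RDT; the five bands; cut-off 10 mg/L (qualitative), and 10 and 40 mg/L (semi-quantitative, third cut-off assumed to be 80); reference test range 5-200 mg/L. Assumed: replicate CV of 10% to 50% (the documents give none), lowest band 0.5-5, top band 80-200, CRP uniform within a band, correct reading, and an RDT that switches at its nominal cut-off. The appendix gives no figure for repeatability, so there is none to reproduce.

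**Distance from 10 mg/L.** 10/5 = 2, 40/10 = 4 and 80/10 = 8. Three samples, or 3 × 5 = 15 of 25 qualitative results, are therefore always at least 2-, 4- and 8-fold away.

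**Model.** Each replicate is log-normal around the true value x, with s² = ln(1 + CV²). For the qualitative RDT, p = Φ(ln(x/10)/s) and P(five agree) = p⁵ + (1 − p)⁵. Averaged over each band:

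| Band (mg/L) | CV 10% | CV 20% | CV 30% | CV 50% |
|---|---|---|---|---|
| < 5 | 1.00 | 1.00 | 0.995 | 0.94 |
| 5 to < 10 | 0.79 | 0.60 | 0.45 | 0.27 |
| 10 to < 40 | 0.96 | 0.91 | 0.86 | 0.73 |
| 40 to < 80 | 1.00 | 1.00 | 1.00 | 1.00 |
| ≥ 80 | 1.00 | 1.00 | 1.00 | 1.00 |
| All five (product) | 0.75 | 0.55 | 0.39 | 0.18 |

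Log-uniform placement changes the products by less than 0.015. Additive error with SD 1, 2, 3 or 5 mg/L gives 0.74, 0.50, 0.30 and 0.10.

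**Effect of placement at CV 30%** (s = √ln 1.09 = 0.294):
- x = 5: p = Φ(−2.36) = 0.009, agreement 0.955. x = 39: agreement 1.00. Product about 0.95.
- x = 9: p = 0.360, agreement 0.360⁵ + 0.640⁵ = 0.114. x = 11: p = 0.627, agreement 0.627⁵ + 0.373⁵ = 0.104. Product about 0.01.

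The other three samples contribute a factor of essentially 1, so these are also the values for the whole set.

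**Semi-quantitative RDT.** With categories cut at 10, 40 and 80, P(five agree) is the sum of the fifth powers of the category probabilities. The product over the five bands is 0.39, 0.11 and 0.02 at CV 10%, 20% and 30%. With cut-offs 10 and 40 only, it is 0.28 and 0.13 at CV 20% and 30%. Four of the five bands adjoin a cut-off if the third is 80.

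**Which placement separates tests better.** Count the discordant replicates per sample (five minus the most frequent result), add them over the five samples, and compare a CV 30% test with a CV 10% test. The AUC is the probability that the less precise test shows the higher count, with ties counted as half.

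| Placement | Qualitative | Semi-quantitative (10, 40, 80) |
|---|---|---|
| As planned | 0.69 | 0.855 |
| Same bands, second sample 7-9, third 11-14 | 0.90 | 0.935 |
| Samples at the cut-offs (1-5, 8-10, 10-12, 36-44, 72-88) | 0.77 | 0.80 |

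**The case against.** The strongest reply is that the design is not as weak as it looks. A reader might infer that perfect repeatability is likely even for an imprecise test. The figures do not support that: for the qualitative RDT, full agreement falls to 39% at CV 30% and 18% at CV 50%, and passes one half only up to a CV of about 20%. For the semi-quantitative RDT it is below one half even at CV 10% if the third cut-off is 80. This part of the objection stands.

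A second reply is that moving samples right up to every cut-off is no cure, because almost any device disagrees there. This also stands: for the semi-quantitative RDT, such samples separate CV 10% from CV 30% less well than the plan does (0.80 against 0.855).

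Third, the appendix also records invalid tests, migration errors, background and line intensity, and replicates across the whole range can show such faults. That is a good reason to keep all five bands. It does not settle the matter, because those readings are described for the 140-sample part and the appendix does not say whether they are taken here.

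Finally, a reader might infer that replicates are read with the CRP value known. The documents are silent on this; all that can be said is that masking is not specified.

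**Conclusion.** The point holds in a limited form. For the qualitative RDT's positive/negative result, only the 5 to < 10 and 10 to < 40 mg/L samples can reveal imprecision at CVs up to about 30%; at 50% the lowest sample begins to contribute slightly. The plan does not control where those two fall, and at CV 30% this alone moves the chance of full agreement between about 0.01 and 0.95. It would go too far to say that the repeatability criterion is left unanswered: the planned set does carry information, with an AUC of 0.69 for the qualitative RDT and 0.855 for the semi-quantitative one.

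The consequence is small. This is a descriptive part of an appendix sub-study, it bears on no primary or secondary objective of the cohort, and a further evaluation is foreseen before routine use. The change is worth considering, not essential. All CVs, the third semi-quantitative cut-off and the log-normal error are assumptions. If an RDT in practice switches at a value other than 10 mg/L, the most informative windows move with it.

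**What to change.** Keep one sample per band, five replicates per RDT and the full CRP range. Add to item 3 of the sample-selection section that the second and third samples should have QuikRead values moderately close to 10 mg/L but not at it, for example about 7-9 and 11-14. Report the number of discordant replicates for each sample and RDT, beside the sample's QuikRead value, and not only whether all five agreed. Where feasible with the readers already at HGK, code the replicate devices so that they are read without the QuikRead value. State whether line intensity is scored in this part.

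The number of samples and devices is unchanged. The cost is a short wait for samples in two narrower CRP windows, plus some device coding. The length of the wait cannot be computed, because the documents give no CRP distribution. HGK must in any case find 14 samples in each of these two bands for the main comparison (70 per site over five bands), unless the split between sites is adapted to recruitment.
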